Couples Health Project: Data Analysis Plan

Development of a couples-based intervention to reduce drug use and enhance sexual health among partnered emerging adults.

NCT# 03386110 LAST UPDATED: 6/1/2021

Analytic plan

A series of bivariate analyses conducted using the generalized estimating equations function within SPSS (version 25) evaluated the success of randomization and the presence of differential attrition. In models evaluating randomization, condition (MI-intervention versus control) served as the sole predictor of baseline characteristics. Analogous models evaluating differential attrition predicted baseline characteristics from a dichotomous variable indicating whether or not a participant completed a specific follow-up.

Multi-level models calculated in Mplus (version 8.2; 48) evaluated primary hypothesized direct treatment effects. These models controlled for the nesting of participants within couples and permitted the specification of logistic and count (Poisson or negative-binomial) distributions as appropriate. Full-information maximum likelihood estimation was utilized to retain all cases in a true intent-to-treat paradigm. For each outcome, 3- and 6-month values were predicted by treatment condition.

The hypothesis that baseline frequency of drug use or CAS with casual partners may moderate the effects of treatment was evaluated using the Actor-Partner Interdependence Model (APIM) framework (49). Models incorporated participants' own baseline report of the outcome (actor scores) as well as their partners' report (partner scores) at Level 1. Interactions among actor and partner baseline scores and treatment condition were also included at Level 1. This included the 3-way interaction term as well as all possible 2-way interactions. A natural log transformation was used to address skew in these predictor variables. For models involving count-distributed outcomes, effect size was calculated using procedures outlined by Larsen and Merlo (50) for the calculation of an Interval Odds Ratio.

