 5.2 Intervention Training and Supervision11

6.0 SAFETY MONITORING PLAN12

 6.1 Data and Safety Monitoring Board.....12

Abbreviations:

TRB – Transmission Risk Behavior
MSM – Men who have Sex with Men
YMSM – Young Men who have Sex with Men
TLFB – Time Line Follow Back
STI – Sexual Transmitted Infection
BL – Baseline appointment
FU – Follow Up appointment

STUDY ABSTRACT

DESIGN: This study utilizes qualitative methods during a formative phase to inform intervention development. Subsequently a small randomized controlled trial is utilized in Phase 2 to evaluate the feasibility, acceptability, and preliminary efficacy of the new intervention relative to an attention-matched education control condition.

SAMPLE SIZE: In Phase 2 we will recruit a sample of 50 couples (n = 100 individuals). At least one member of the couple must be a YMSM between the ages of 18 and 29; report recent (past 30 days) drug use; and recent (past 30 day) Transmission Risk Behavior (TRB).

POPULATION: Partnered MSM aged 18-29 who are in a primary relationship with another man for at least 3 months, who also uses some kind of illicit drug, and also had some TRB in the last 30 days with a casual partner or with a non-monogamous serodiscordant partner. In addition all participants will have to be able to communicate in English.

STRATIFICATION: Participants will be randomized at baseline to receive their first CHP or Education session directly following their baseline appointment. The study will employ a stratified randomization procedure using Qualtrics.

DATA COLLECTION: Participants have the options to first complete a brief CASI at home before or during their BL appointment. Regardless, they will then complete another survey at their BL appointment along with a TLFB, STI testing (Gonorrhea & Chlamydia Urethral and Rectal), and Drug testing. During session 3, participants will complete a CHTC session that involves Rapid HIV testing for couples. For 1m FU participants will complete an at home Qualtrics survey. At 3M FU participants will complete a Qualtrics survey, a TLFB and a Fingernail specimen collection for drug use.

[figure not shown]
Study Procedure Guide (SPG)

Finally, at 6M FU participants will complete a Qualtrics survey, a TLFB and Specimen collection to test drug use on fingernail sample and Gonorrhea & Chlamydia for STI testing (Urethral and Rectal).

OBJECTIVES

- 1) Develop content to address PrEP uptake/adherence and integrate biological testing

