- 2) Evaluate the efficacy, feasibility, and acceptability of CHP at 3- and 6-month follow-up.

STUDY DESIGN:

Original Study Timeline:

Month	Year 1					Year 2		Year 3	
	1-2	3-4	5-8	9	10-12	13-18	19-24	25-30	31-36
Planned activity									
Phase I: intervention development									
Startup	■								
Interviews with partnered YMSM (n = 20)		■							
Qualitative data analysis			■						
Intervention development and staff training				■					
Phase II: enrollment									
Enrollment (n = 50 couples; 100 individuals)						■	■	■	■
Follow up data collection						■	■	■	■
Data analysis									
Dissemination of qualitative findings						■			
Intervention outcome analyses									■

STUDY POPULATION

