4.3 Randomization Process/Systems

Participants will be randomized at the end of their baseline assessment into one of two control conditions: 1) delivery of the 3 session CHP intervention or 2) delivery of a 3 education sessions. Each participant's condition will be tracked in the access tracking database maintained by the Research Coordinator.

The study will employ a stratified randomization procedure for each interventionist using Qualtrics. Randomization will be stratified on:

1. Age discrepancy Question: is the couples age difference (3 years or less/ longer than 3 years)
2. Relationship Length Question: is the couple's relationship length (2 years or less/longer than 2 years)
3. Racial makeup question: is the couples racial makeup (both partners identify as white and non-Hispanic/one or both partners identify as nonwhite or Hispanic)

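### The attrition check leaves out condition and the primary models, as written, leave out the baseline outcome, so dropout by arm is not shown and baseline-related dropout is not handled in the direct treatment comparison

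*SAP*

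**What the plan says.** The SAP's Analytic plan sets out two sets of bivariate GEE models. The first checks randomization, with condition as the only predictor of each baseline characteristic. The second is the attrition check: "Analogous models evaluating differential attrition predicted baseline characteristics from a dichotomous variable indicating whether or not a participant completed a specific follow-up".

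For the primary direct effects it says: "For each outcome, 3- and 6-month values were predicted by treatment condition". Nesting within couples is handled, and the models "permitted the specification of logistic and count (Poisson or negative-binomial) distributions as appropriate". On missing data: "Full-information maximum likelihood estimation was utilized to retain all cases in a true intent-to-treat paradigm". No baseline value, other covariate, auxiliary variable or missingness assumption is named for these models.

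Own and partner baseline scores enter only the separate APIM models, which test "The hypothesis that baseline frequency of drug use or CAS with casual partners may moderate the effects of treatment".

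The protocol's second objective is to "Evaluate the efficacy, feasibility, and acceptability of CHP at 3- and 6-month follow-up". Protocol 4.5 provides for general retention reports. Neither document plans a comparison of completion by condition.

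**The concern.** There are two linked problems.

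**The check does not answer the question its name implies.** Comparing completers with non-completers over both arms together cannot reveal unequal dropout between arms. It can miss selection that runs in opposite directions, and it picks up one-arm selection only some of the time. It can also reject when selection is the same in both arms, which leaves the contrast unbiased unless the treatment effect varies with baseline. No decision hangs on the check, so its form biases no estimate. The risk is that a clean result is read as evidence that the arms lost comparable people.

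**The bias risk lies in the primary models.** With condition as the only named predictor, the likelihood contains nothing that links dropout to baseline drug use or CAS. A participant with neither follow-up value adds nothing to the treatment estimate, despite the statement that all cases are retained. If heavier users leave CHP, the contrast favours CHP; if they leave education, it runs against CHP. The SAP itself hypothesises that the effect varies with baseline, and in that case even equal selection in both arms shifts the average effect.

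**Working it through.** **What each model contains, as written in the SAP**

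| Model | Outcome | Predictors named |
|---|---|---|
| Randomization check | baseline characteristic | condition |
| Attrition check | baseline characteristic | completion (yes/no) |
| Primary | 3- and 6-month value | condition |
| APIM moderation | outcome | condition, own and partner baseline, all interactions |

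**Inputs.** The protocol's Study Abstract gives 50 couples (100 individuals). The documents give no dropout rate, correlation, alpha or power, so there is no planned figure to reproduce and everything else is assumed: 25 couples per arm, continuous outcome with SD 1, true effect 0, within-couple correlation 0.3, baseline-outcome correlation ρ = 0.6, dropout r = 22%, dropout odds ratio (OR) 2 to 3 per baseline SD. Whether partners leave singly or together is not stated, so paired results are individual/couple dropout. For couple dropout the OR acts on the couple mean, whose variance is v = (1 + 0.3)/2 = 0.65; for individual dropout v = 1.

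**Bias of the unadjusted contrast.** With logistic dropout probability p and k = ln(OR), the completers' mean baseline score in an arm is

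m = −v · k · E[p(1−p)] / (1 − r), and bias = ρ · (m in CHP − m in education).

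E[p(1−p)] comes from numerical integration, with the intercept set to give 22% dropout.

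- OR 2, individual: m = −0.693 × 0.159 / 0.78 = −0.141; CHP-only bias = 0.6 × −0.141 = −0.085.
- OR 2, couple: m = −0.65 × 0.693 × 0.163 / 0.78 = −0.094; bias −0.056.
- OR 3, individual: m = −1.099 × 0.144 / 0.78 = −0.203; bias −0.122.
- OR 3, couple: m = −0.65 × 1.099 × 0.152 / 0.78 = −0.139; bias −0.083.
- Opposite selection doubles each: −0.169/−0.113 at OR 2 and −0.243/−0.167 at OR 3.

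Simulation at the trial's size (4000 runs per case, cluster-robust tests) agrees:

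| Dropout pattern | Unadjusted bias, SD | Type I error | Planned check rejects |
|---|---|---|---|
| CHP-only, OR 2 | −0.087/−0.062 | 6.9%/5.1% | 27%/14% |
| CHP-only, OR 3 | −0.131/−0.085 | 8.0%/7.0% | 47%/23% |
| Opposite, OR 2 | −0.171/−0.115 | 10.2%/7.6% | 5%/6% |
| Opposite, OR 3 | −0.249/−0.164 | 17.2%/9.9% | 4%/6% |
| Same in both arms, OR 2 | 0.00 | – | 77%/38% |
| Same in both arms, OR 3 | 0.00 | – | 98%/67% |

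With 35% v 10% dropout and selection, the bias is −0.124/−0.087 at OR 2 and −0.187/−0.137 at OR 3. Over correlations 0.4–0.7, within-couple correlations 0.1–0.5 and dropout 15–30%, the size of the bias runs from 0.03 to 0.19 SD (CHP-only) and 0.03 to 0.38 SD (opposite).

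**Why the check misses these patterns.** Baseline has mean 0 in each arm, so with equal selection the completer minus non-completer gap is m/r = −0.141/0.22 = −0.64 SD (couple: −0.094/0.22 = −0.43 SD). The check rejects although the contrast is unbiased. With opposite selection the two arms' gaps cancel. With 10% v 35% dropout unrelated to baseline there is no gap, and the check rejects at about its no-selection rate (6.4%/7.0% against 5.9%/6.7%).

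**If the effect varies with baseline.** With moderation of γ SD per baseline SD and equal selection, the average effect shifts by γ · m. For γ = 0.5 and OR 2 this is 0.5 × −0.141 = −0.07 (couple −0.05); simulation gives −0.076/−0.055. A main-effect baseline covariate leaves it at −0.075/−0.054. A condition-by-baseline term averaged over everyone enrolled brings it to within 0.006.

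**Count and binary outcomes.** SD figures do not carry over, so these were run separately with marginal models, not the Mplus random-intercept models. For a count with assumed mean 5 and true rate ratio 1, OR 2 to 3 gives rate ratios of 0.90–0.84/0.93–0.89 (CHP-only) and 0.81–0.75/0.87–0.82 (opposite). For a binary outcome (5 or more, true odds ratio 1), CHP-only selection gives 0.88–0.79/0.90–0.85.

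**With the baseline outcome in the model and no moderation.** Bias is at most 0.010 SD at the central settings and 0.021 across the range, type I error is 4.5–6.0%, rate ratios are 0.98–1.01 and odds ratios 0.97–1.02.

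**The case against.** The SAP is a short, past-tense summary. It uses sole-predictor wording for the randomization check but not for the primary models, so baseline may have been included and simply not mentioned. That is possible, and is why the point is limited to the models as written; if baseline was used, one sentence settles it.

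The APIM models do contain baseline scores. True, but they test moderation, and their condition coefficient is conditional on interaction terms, so they do not replace the primary effect.

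The central bias is modest. The unadjusted contrast has a standard error of about 0.25 SD under these assumptions, so 0.06 to 0.09 SD is roughly a quarter to a third of it, and CHP-only type I error at OR 2 is near nominal. The larger errors need opposite selection, which is extreme. This stands, and it limits the severity.

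Modelling both follow-ups jointly would let a 3-month value inform a missing 6-month one. In one run (assumed 3-to-6-month correlation 0.7, half of dropout after month 3) this cut the 6-month bias from 0.089 to 0.057 SD. The SAP does not say whether the follow-ups are joint, and dropout before month 3 is not covered either way.

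A test of completion by arm would be weak: for 10% v 30% dropout, power is 42% with the couple as unit. That argues for reporting an estimate with its interval rather than relying on a test. Retention by arm still bears on the feasibility aim.

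**Conclusion.** The concern holds on the text. The attrition models have no condition term, the primary models name no baseline outcome, and nothing compares completion by arm. The documents do not show that bias occurred.

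Unequal dropout rates alone would not bias the contrast. Baseline-related dropout does so when its relation to baseline differs by arm, or when the effect varies with baseline. On the assumed inputs, one-arm selection at OR 2 to 3 costs about 0.06 to 0.13 SD, or a spurious rate reduction of 7% to 16% for a count outcome. Opposite selection is worse and almost invisible to the planned check. This should be fixed: the bias is modest in the likelier cases, but the remedy is nearly free. In the same continuous setting it also cut the standard error from about 0.25 to 0.20 SD.

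**What to change.** 1. **Name the baseline value of each outcome as a covariate in every 3- and 6-month primary model.** State whether the two follow-ups are modelled jointly, and state the missingness assumption. If the models have already been run, show unadjusted and adjusted results side by side and label the adjusted ones as added.
2. **Report completion at 3 and 6 months by condition**, with the difference and a couple-clustered 95% CI. Do this separately for survey/TLFB and for specimens, because Protocol 4.7.1 records that specimen collection stopped on 3/15/2020 while surveys continued.
3. **Relabel the pooled models** as a description of who drops out, and add a table of baseline outcome values for completers and non-completers within each arm. If a condition-by-completion interaction is also fitted, use a small-sample-corrected standard error. With no selection, the usual robust error rejected 6.6%/9.2% at 22% dropout and 9.3%/12.5% at 10% v 35%; a leave-one-couple-out correction gave 4.6%/4.0% and 5.2%/7.1%.
4. **As a secondary estimate, average the condition effect from the planned APIM models over the baseline scores of all enrolled participants.** This addresses the moderation shift that a main-effect covariate leaves in place. It was checked for continuous outcomes with the partner and three-way terms included; for count and logistic models the SAP must also state the scale of averaging.

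The cost is SAP wording, one table and a few model runs. The baseline data exist (participants "complete another survey at their BL appointment along with a TLFB", Protocol, Study Abstract), arm is recorded ("condition will be tracked in the access tracking database maintained by the Research Coordinator", Protocol 4.3), and Protocol 4.5 tracks completion. The drawback is a wide interval for the completion difference. At 22% dropout the half-width is about 1.96 × √(2 × 0.22 × 0.78/50) = 0.16 for individual dropout and, with 25 couples per arm, 0.23 for couple dropout; simulation gave 0.165 and 0.233.

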3.1 Inclusion and Exclusion Criteria

a. Inclusion

- i. One partner must be 18 to 29 years of age
- ii. Both partners born male and currently identify as male
- iii. One partner must be HIV-negative (one partner can be HIV positive)
- iv. In a relationship with another man for at least 3 months
- v. Either partner reporting the use of at least one of the following substances in the past 30 days Marijuana, cocaine and crack, amphetamines, ecstasy, GHB, ketamine, nitrates
- vi. Either partner reporting CAS with a casual partner and/or CAS with a non-monogamous or serodiscordant main partner in past 30 days.
- vii. Must be able to communicate English
- viii. Must reside in the NYC metro area

b. Exclusion

- i. Either member of the couple reports IPV, which is defined as serious physical or sexual violence that occurs outside the context of consensual bondage or sado-masochistic sexual play, which results in concerns of safety (IPV-GBM scale)
- ii. Unstable, serious psychiatric symptoms
- iii. Currently suicidal/homicidal
- iv. Evidence of gross cognitive impairment

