4.6 Retention and Follow Up

Intervention visits: For participants who are actively taking part in the CHP intervention or Education condition their assigned clinician or educator will be charged with scheduling sessions and rescheduling missed sessions. Participants will be reminded 1 day prior to their scheduled sessions by a study staff.

Research visits: Study staff will maintain strong and consistent relationships with study participants, and should contact study participants by text, phone, and/or email at minimum once per every follow up assessment to assure follow up scheduling and attendance. During this phone outreach, site study staff can verify existing contact information. Study staff should take note of participants who are less stable in terms of contact information i.e. Phone number/e-mail address, and devote outreach efforts toward these participants strategically.

***NOTE: Due to COVID-19, all follow-up assessments completed after 3/15/2020 were conducted remotely via Zoom and online survey administration via Qualtrics.

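### The SAP says full-information maximum likelihood keeps every case, but its stated primary models include no baseline value, so men without follow-up add nothing and the missing-data assumption is unstated

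*SAP*

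**What the plan says.** The SAP's Analytic plan says that "Full-information maximum likelihood estimation was utilized to retain all cases in a true intent-to-treat paradigm". The sentence after it gives the whole of the stated primary specification: "For each outcome, 3- and 6-month values were predicted by treatment condition". The couple is the level of nesting, and logistic or count distributions are used as appropriate.

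Baseline appears in two other places in the SAP:

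- The attrition check: "Analogous models evaluating differential attrition predicted baseline characteristics from a dichotomous variable indicating whether or not a participant completed a specific follow-up". No step carries its result into the primary models.
- The Actor-Partner Interdependence Models (APIM), which test "The hypothesis that baseline frequency of drug use or CAS with casual partners may moderate the effects of treatment". These contain own and partner baseline scores, log-transformed for skew, with every interaction with condition.

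The baseline measurement exists. In the protocol's Study Abstract, under Data Collection, participants attend baseline and "they will then complete another survey at their BL appointment along with a TLFB". The SAP does not say whether the two follow-up visits are modelled jointly or whether auxiliary variables were used.

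**The concern.** Full-information maximum likelihood uses only the variables in the model. If the model holds only follow-up values, condition and couple membership, a man with no follow-up has nothing in it for the likelihood to use. The claim that all cases are kept then does not describe what the stated model does.

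The assumption behind the result also becomes stronger than it need be. Dropout must be unrelated to the missing outcome given arm and the observed follow-up values of the man or his partner, with no help from his own baseline. Baseline is likely to vary widely between men, since section 3.1 of the protocol requires only "Either partner reporting the use of at least one of the following substances in the past 30 days".

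Two things are at stake. A reader cannot tell how many men support the primary estimate, and if baseline predicts both dropout and outcome, the estimate can be shifted.

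**Working it through.** The documents give no power calculation, dropout rate or correlation, so there is no figure of the plan's own to reproduce. From the documents come the model (SAP, Analytic plan), 50 couples or 100 men (Study Abstract), and the hypothesis that baseline moderates the effect (SAP). Everything else below is assumed.

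**Step 1: contribution of a man with no follow-up.** His observed-data likelihood is the density of his two values, given his partner's, integrated over both. Numerical integration gives 1.000, so his log-likelihood contribution is log 1 = 0, whether or not his partner was seen. If 10%, 20% or 30% of men had no follow-up, 90, 80 or 70 of 100 would inform the effect. If the visits are modelled separately, a man missing one visit also adds nothing to that visit's model.

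**Step 2: large-sample bias.** Let the baseline B be standard normal, r the baseline-outcome correlation, g the change in effect per baseline SD, and the average effect zero. Dropout is logistic in B. Write m for the mean of B among completers in an arm. The unadjusted estimate tends to

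(r + g) × m(CHP) − r × m(education).

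With a dropout log-odds slope of 1 per SD, numerical integration gives m = −0.133, −0.189 and −0.245 at 15%, 22% and 29% dropout. With slope 0, m = 0. Absolute bias in SD:

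| Case | Arithmetic, r = 0.6 | Bias at r = 0.6 | Bias at r = 0.3 |
|---|---|---|---|
| Dropout tied to baseline in one arm only, 22% | 0.6 × 0.189 | 0.11 | 0.06 |
| Same slope, 15% vs 29% | 0.6 × (0.245 − 0.133) | 0.07 | 0.03 |
| Same slope and rate (22%), g = 0.5 | 0.5 × 0.189 | 0.09 | 0.09 |
| Same slope and rate, g = 0 | 0.6 × 0 | 0 | 0 |

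**Step 3: what adding baseline does (large-sample simulation, r = 0.6).**

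- One arm only, 22%: 0.113 falls to 0.001 with a baseline main effect.
- 15% vs 29%: 0.067 falls to 0.001.
- Effect varying with baseline (g = 0.5, 22%): 0.094 without baseline and 0.093 with a main effect. Completers have the same baseline mean in both arms, so a main effect has no imbalance to correct. The shift arises because the effect is averaged over completers rather than over all randomised men. A condition-by-baseline term centred on all randomised men brings it to 0.002.

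**Step 4: modelling the two visits jointly, without baseline.** At r = 0.6 with one-arm dropout of 22%, the 6-month bias is 0.11 if the same men miss both visits. It is 0.06-0.07 if visits are missed independently given baseline. Joint modelling of the visits alone does not remove it.

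**Step 5: scale against noise.** In simulations of 50 couples at r = 0.6, the SD of the unadjusted estimate is about 0.26, so a bias of 0.11 is 0.11/0.26 ≈ 0.4 of a standard error. Type I error in the first two cases was about 6 to 7.5%, and 4.7 to 6.2% with own and partner baseline.

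**Step 6: precision on the planned scales (simulation, assumed settings).** For count outcomes the standard error fell with baseline added (0.31 to 0.26 in one setting, 0.47 to 0.28 in another). For a logistic outcome the standard error of the log odds ratio rose from 0.46 to 0.50, while the ratio of effect to standard error improved from 1.15 to 1.20.

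**The case against.** The strongest reply is that the SAP is silent rather than wrong. It says explicitly that condition was the only predictor in the randomisation check, but does not say so of the primary models, so covariates or auxiliary variables may have been used without being described. That stands: baseline is not stated in the primary models, and a reader should not infer that it was shown to be left out. The claim about keeping all cases still has no support in the specification given.

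Second, the APIM models already condition on baseline and let the effect vary with it. This also stands, and the fix uses it. But the SAP presents them as tests of moderation, not as the source of the primary effect. With baseline as a predictor only, a man with no follow-up still adds nothing to them.

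Third, the SAP checks attrition against baseline. The check is useful, but as described it pools the arms. In simulations of 50 couples under the assumptions above, it flagged 95% of trials with equal slopes and rates, where there is no bias without effect variation, and 41% of those with dropout tied to baseline in one arm.

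Fourth, the magnitudes are assumed, and this is a small trial of feasibility, acceptability and preliminary efficacy. Both are true, and they limit the weight of the point.

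A reader might also infer that men were analysed outside their randomised arm, or that the COVID-19 changes emptied the follow-up data. The documents support neither. Nothing suggests departure from the allocated arm, and section 4.6 records that "all follow-up assessments completed after 3/15/2020 were conducted remotely via Zoom and online survey administration via Qualtrics". The specimen suspension matters only for a biological outcome, and the SAP names none.

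**Conclusion.** The point holds in a limited form. As specified, the primary models do not keep men without follow-up, and the missing-at-random assumption they rest on is not stated. It should be corrected, but it is not evidence that the result is wrong.

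The size is about 0.07-0.11 SD when baseline-related dropout differs by arm, and about 0.09 SD when the effect varies with baseline. Both figures assume 15-29% dropout, a log-odds slope of 1 per SD and a normal outcome; the first also assumes r = 0.6 and the second an effect change of 0.5 SD per baseline SD. At r = 0.3 the first range is halved. The trial's models are logistic or count, so these figures do not convert directly to odds or rate ratios. If dropout is related to baseline equally in both arms and the effect is constant, there is no bias.

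Two tempting extensions fail. Adding baseline is not a complete cure: a main effect leaves the moderation case untouched. If dropout in one arm (22%) depends half on the outcome itself, adjustment only reduces bias, from 0.13 to 0.09 at r = 0.3 and from 0.16 to 0.07 at r = 0.6. Nor does adding baseline shrink every standard error, as the logistic check shows.

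**What to change.** 1. Add own and partner baseline values of the outcome, log-transformed as in the APIM models, to the primary models. Alternatively, model baseline jointly with follow-up; only this version lets men with no follow-up contribute. If analyses are complete, report it as a labelled sensitivity analysis.
2. Because moderation is hypothesised, also report the average effect from a model with condition-by-baseline terms, with baseline centred on, or averaged over, all randomised men. The existing APIM model can supply this.
3. Replace the claim that all cases are kept with the missing-at-random assumption actually made. Say whether the visits are modelled jointly and list any auxiliary variables. Report the men and couples contributing to each model, by arm.

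The cost is SAP wording and one re-run on data already collected. The downside is that, for logistic outcomes, the adjusted odds ratio is conditional and its standard error may be larger, so a standardised (marginal) effect should be reported beside it. Expect a precision gain for count outcomes, and for logistic outcomes only a modest gain in power.

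### The direct-effect models name treatment as their only predictor, so baseline drug use and CAS, measured before randomisation, go unused and precision may be lost

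*SAP*

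**What the plan says.** The SAP (Analytic plan, second paragraph) gives the primary direct effects to multilevel models that account for couples and allow logistic or count distributions. On predictors it says only: "For each outcome, 3- and 6-month values were predicted by treatment condition".

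Baseline values enter in the third paragraph, which tests another question: "The hypothesis that baseline frequency of drug use or CAS with casual partners may moderate the effects of treatment". Those models hold the participant's own and the partner's baseline score: "Interactions among actor and partner baseline scores and treatment condition were also included at Level 1", with every two-way term and the three-way term. On scaling: "A natural log transformation was used to address skew in these predictor variables". No centring, reference value, averaging or log offset is given.

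On timing, the Protocol's Study Abstract (Data Collection) says of participants that "they will then complete another survey at their BL appointment along with a TLFB, STI testing" and drug testing. Section 4.3 says "Participants will be randomized at the end of their baseline assessment". The strata in section 4.3 are age difference, relationship length and racial makeup; drug use and CAS are not among them. Planned enrolment is 50 couples (100 individuals). The Protocol has no statistical section that adds an adjusted model.

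**The concern.** A participant's own baseline frequency is usually an obvious candidate to predict later frequency of the same behaviour. Here it is collected before allocation, so it is a valid covariate, yet it is not named in the models that estimate the treatment effect. With about 25 couples per arm, chance differences in baseline drug use or CAS are to be expected, and the strata do not control them. The SAP's checks on the success of randomisation would describe such a difference but would not take it out of the estimate.

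The models that do contain baseline are built to test moderation. Unless their baselines are centred or the effect is averaged, their treatment coefficient does not supply the missing adjusted average effect. At stake is the width of the interval around the main estimate and the clear reading of one coefficient. Bias is not at stake.

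**Working it through.** The documents state no alpha, power, effect size, ICC, dispersion, retention or baseline-outcome correlation, so there is no figure of the plan's own to reproduce. Everything below except the 50 couples is assumed.

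**1. Continuous approximation.** Inputs: 50 individuals (25 couples) per arm, ICC 0.3, two-sided alpha 0.05, 80% power (1.96 + 0.84 = 2.80).

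- SE of the difference in SD units: sqrt(2 × (1 + ICC)/50) = sqrt(2 × 1.3/50) = 0.228.
- Detectable difference, treatment only: 2.80 × 0.228 = 0.64 SD.
- Adjustment for baseline multiplies the SE by sqrt(1 − r²).

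| r | sqrt(1 − r²) | SE reduction | Detectable difference |
|---|---|---|---|
| 0.3 | 0.954 | 5% | 0.61 SD |
| 0.5 | 0.866 | 13% | 0.55 SD |
| 0.7 | 0.714 | 29% | 0.46 SD |

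At ICC 0.1 and 0.5 the treatment-only figure is 0.59 and 0.69 SD; the percentage reductions do not change.

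If the baseline has the same ICC, one standard error of chance imbalance is also 0.228 SD. It moves the treatment-only estimate by about r × 0.228: 0.07, 0.11 and 0.16 SD at the three values of r.

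**2. Counts by simulation.** Settings: 50 couples, Poisson counts with median rate 3, log-scale variance 1 (30% of it between couples), negative-binomial model with a couple random intercept, 2,000 runs per cell. The SD of the log rate ratio is taken under no effect. Power is for a rate ratio of 0.5, using a permutation test so that both models are compared at about the same type I error.

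| Observed r of log counts | SD, treatment only | SD, + own and partner ln(1+count) | Change | Power |
|---|---|---|---|---|
| 0.22 | 0.266 | 0.261 | −2% | 65% to 67% |
| 0.36 | 0.264 | 0.241 | −9% | 63% to 71% |
| 0.51 | 0.263 | 0.218 | −17% | 65% to 83% |
| 0.63 | 0.268 | 0.188 | −30% | 63% to 91% |

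Simulation error is about sqrt(0.65 × 0.35/2000) = 1 point, so the first row shows no useful gain. With 20% of couples lost at random (1,500 runs), power goes from 54 to 57%, 56 to 63%, 54 to 72% and 57 to 85%.

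**3. Binary outcomes by simulation.** With a conditional odds ratio of 0.4 and observed r of 0.09, 0.15, 0.21 and 0.26, power goes from 28 to 28%, 30 to 28%, 29 to 30% and 30 to 31%. The SD of the log odds ratio rises 4 to 5% with adjustment. No benefit is shown.

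**4. Moderation models.** Let T be treatment, and A and P the logged own and partner baselines. The treatment effect at A = a, P = p is

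b_T + b_TA·a + b_TP·p + b_TAP·a·p.

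Uncentred, the reported coefficient b_T is the effect at a = p = 0. That is a count of 0 for both partners under ln(1+count), or a count of 1 for both under plain ln. As an illustration, take b_T = 0, b_TA = −0.2, b_TP = −0.1, b_TAP = 0, with means of A and P of 1.341 and 1.343. The average log rate ratio is −0.2 × 1.341 − 0.1 × 1.343 = −0.40, a rate ratio of 0.67. The uncentred coefficient gives 1.00.

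**5. Zero counts.** Criteria v and vi (Protocol 3.1) can be met by either partner, so the other may have a count of zero, where plain ln is undefined. As each row holds own and partner scores, one zero affects both rows of that couple. Under the count settings in step 2, 14% of participants and 25% of couples have at least one zero. Losing those rows would conflict with the SAP's aim of retaining all cases.

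**The case against.** The strongest reply is that nothing wrong has been shown. The Protocol describes a small trial to "evaluate the feasibility, acceptability, and preliminary efficacy of the new intervention" and sets no power target. The treatment-only contrast is valid under randomisation. Every gain above rests on assumed values and disappears when r is low. The continuous formula matches neither of the non-normal families that the SAP names. The SAP, dated 6/1/2021, is written in the past tense, so an adjusted model added now cannot be called prespecified. All of this stands, and it limits the point to precision and to a clearly labelled additional result.

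A reader might also infer four stronger things that the documents do not support:

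- *That the SAP rules covariates out.* It speaks of a sole predictor only for the randomisation checks. For the direct-effect models it names treatment and says nothing about others.
- *That the SAP offers the moderation coefficient as an average effect.* It never does. Those models test moderation, and centring leaves the three-way term unchanged. The centring point is therefore secondary.
- *That a zero baseline for both partners is a profile almost no enrolled couple has.* For casual-partner CAS this fails, because criterion vi also admits couples through CAS with a non-monogamous or serodiscordant main partner. For drug use it would need a ln(1+count) scale and an outcome covering every substance in criterion v; the SAP states neither.
- *That every outcome should be adjusted.* For binary outcomes step 3 shows no gain, and adjustment changes the estimate to a conditional odds ratio.

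**Conclusion.** The point holds as a matter of efficiency and clarity. The primary models, as described, leave out baseline drug use and CAS, which are measured before randomisation and not balanced by the strata. A reader might take this to mean that the treatment-only estimate is biased. It is not; it is exposed to chance imbalance and may be less precise than it could be.

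The size is uncertain. The standard error would fall by about 5% to 29% for r from 0.3 to 0.7 under the continuous approximation with ICC 0.3. The count simulation gives 2% to 30% for observed r from 0.22 to 0.63. Near r = 0.2 there is no useful gain for counts, and none was shown for binary outcomes. All r, ICC and dispersion values are assumptions.

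That the uncentred moderation coefficient differs in meaning from an average effect follows from the algebra and needs no assumed correlation. How far the two differ in value depends on the interactions, which are unknown.

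**What to change.** - **Direct-effect models.** State which covariates they contain. For the count outcomes measured at baseline (drug use, CAS), add the participant's own and the partner's baseline as ln(1+count), without interactions. Report the result beside the treatment-only result, and label it a sensitivity analysis unless it was specified before outcomes were seen.
- **Moderation models.** Mean-centre the logged baselines, or report the treatment effect averaged over the baseline distribution. State the log offset, and choose one that keeps zero counts, such as ln(1+count).

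The cost is a short SAP paragraph and one more set of runs on data already held. The adjusted models carry two extra parameters and gain little if baseline is weakly prognostic. If the effect varies with baseline, the adjusted and treatment-only rate ratios are not the same quantity (0.47 and 0.45 in a simulation whose true average was 0.49), so the report should say which is which.
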